9 PRIVACY AND CONFIDENTIALITY

9.1 Privacy protections. Describe the steps you will take, if any, to address possible privacy concerns of subjects and potential subjects.

Privacy refers to the sense of being in control of access that others have to ourselves. This can be an issue with respect to recruiting, consenting, sensitivity of the data being collected, and the method of data collection. Examples:

- Many subjects will feel a violation of privacy if they receive a letter asking them to participate in a study because
 they have ____ medical condition, when their name, contact information, and medical condition were drawn from
 medical records without their consent. Example: the IRB expects that "cold call" recruitment letters will inform the
 subject about how their information was obtained.
- Recruiting subjects immediately prior to a sensitive or invasive procedures (e.g., in an outpatient surgery waiting room) will feel like an invasion of privacy to some individuals.
- Asking subjects about sensitive topics (e.g. details about sexual behavior) may feel like an invasion of privacy to some individuals.

The PI and other physicians who refer/recruit for the study generally ask the patient first if they are interested in hearing more about a research study they may be eligible for. When screening by phone, the study staff will perform phone calls to the contact number listed in the medical record during business hours. No messages will be left if the patient is not available.

We are always willing to describe the measures we take to protect their information and answer questions from subjects about where we received their contact information. We stress the voluntary nature of the study and that they can stop participating at any time.

information about subje	uals in publications and presentations. Do you plan to use potentially identifiable cts in publications and presentations, or is it possible that individual identities could be plan to publish or present?
X No Yes → If yes, will ye	ou obtain subject consent for this use?
No	→ If no, describe the steps you will take to protect subjects (or small groups of subjects) from being identifiable.

9.3)State mandatory reporting. Each state has reporting laws that require some types of individuals to report some kinds of abuse, and medical conditions that are under public health surveillance. These include: Child abuse Abuse, abandonment, neglect, or financial exploitation of a vulnerable adult Sexual assault Serious physical assault Medical conditions subject to mandatory reporting (notification) for public health surveillance Are you or a member of your research team likely to learn of any of the above events or circumstances while

conducting your research AND feel obligated to report it to state authorities?

•		ing your research with reer obligated to report it to state authorities.
	X No	
	Yes	→ If yes, the UW IRB expects you to inform subjects of this possibility in the consent form or during the consent process, unless you provide a rationale for not doing so:
_	 	

9.4) Retention of identifiers and data. Check the box below to indicate your assurance that you will not destroy any identifiers (or links between identifiers and data/specimens) and data that are part of your research records until after the end of the applicable records retention requirements (e.g. Washington State; funding agency or sponsor; Food and Drug Administration) for your research. If you think it is important for your specific study to say something about destruction of identifiers (or links to identifiers) in your consent form, state something like "the link between your identifier and the research data will be destroyed after the records retention period required by state and/or federal law."

This question can be left blank for conversion applications (existing paper applications that are being "converted" into a *Zipline application.)*

See the "Research Data" sections of the following website for UW Records management for the Washington State research rectords retention schedules that apply in general to the UW (not involving UW Medicine data): http://f2.washington.edu/fm/recmgt/gs/research?title=R

See the "Research Data and Records" information in Section 8 of this document for the retention schedules for UW Medicine Records: http://www.uwmedicine.org/about/Documents/UWMRRS-1.5.pdf

Confirm

9.5) Certificates of Confidentiality. Do you have or, are you planning to obtain, a federal Certificate of Confidentiality for your research data?

No Yes

9.6. [DETERMINATION] Data security protections. Identify the data risk level and the security protections that will be provided for all sites where data will be collected, transmitted, or stored. All data in the same system should be maintained at the highest risk level of any type of data. For example, if some of the data are level 1 (L1) and some are level 3 (L3), then the whole system should be protected at level 3 (L3).

9.6.a. Choose the level(s) of protections you will apply to the data. Refer to the WEBPAGE Data Security Requirements Guidance to answer this question.

□ Level 1	
□ Level 2	
☑ Level 3	
□ Level 4	
If you checked more than one box above, use the text box to describe which level will apply to which data and in which system and/or site(s) it will be stored.	1
Click or tap here to enter text.	

9.6.b. HSD allows researchers to request exceptions to data security requirements, if the exception is necessary and does not significantly increase risk to participants. If there are data security requirements within the selected risk level(s) listed in 9.6.a which will not be followed, list those here. Specify the data and the system or site(s) where this exception will apply. Provide a rationale for the exception and explain what (if any) alternative measures will be taken to protect the data.

Example - If you intend to store subject identifiers with study screening data (not permitted under requirement U9 for Risk Levels 3-4), then indicate this in the box below (e.g., "We will not adhere to requirement U9 for screening data because we are capturing this in REDCap via subject surveys which maintains the data together. The REDCap system has other sufficient security measures that we feel mitigates the risk of maintaining the information together").

Click or tap here to enter text.

10 RISK / BENEFIT ASSESSMENT

- **10.1** Anticipated risks. Describe the reasonably foreseeable risks of harm, discomforts, and hazards to the subjects and others of the research procedures. For each harm, discomfort, or hazard:
 - Describe the magnitude, probability, duration, and/or reversibility of the harm, discomfort, or hazard, AND
 - Describe how you will manage or reduce the risks. Do not describe data security protections here, these are already described in Question 9.6.
 - Consider physical, psychological, social, legal, and economic risks, including risks to financial standing, employability, insurability, educational advancement or reputation.
 - Examples of "others": embryo, fetus, or nursing child; family members; a specific group.
 - Do not include the risks of non-research procedures that are already being performed.
 - If the study design specifies that subjects will be assigned to a specific condition or intervention, then the condition or intervention is a research procedure even if it is a standard of care.
 - Examples of mitigation strategies: inclusion/exclusion criteria; applying appropriate data security measures to prevent unauthorized access to individually identifiable data; coding data; taking blood samples to monitor something that indicates drug toxicity.
 - As with all questions on this application, you may refer to uploaded documents.

Injury from the Hardware: The risk of injury related to the hardware equipment is minimal. The investigational device is comprised of four principle commercially available off-the-shelf components: the Verasonics data acquisition system (VDAS), ultrasound transducer, host computer, and driving software. The transducers are commercially available FDA cleared devices purchased used from a compliant source. The computer is an off the shelf commercially available PC. The VDAS unit is available through Verasonics Inc., and has previously received IRB approval within the UW for use below the FDA acoustic output intensities. Verasonics has prepared

a risk analysis for its device (uploaded to Zipline). The driving software includes Windows operating system and MATLAB computing software.

The equipment is inspected (annually) by the University of Washington Science and Instrumentation Division for electrical safety. This includes an evaluation of electrical leakage from each individual piece of equipment and the transducer, ground impedance, and line isolation. Users will conduct a visual check of the equipment, ultrasound transducer, and AC lines prior to starting the system to verify the system is in good operating order. If damage is observed, the user will replace the damaged item (if it is within their abilities), or contact someone who can.

Upon startup of the program a routine will be automatically initiated that tests for damage to the transducer elements. A log will be kept of these test results and a message placed on screen to notify the user if the study should be aborted. The output of the Push pulse will be test using a phantom to verify the output of the push pulse is within specification. The time delay allowed between Push bursts will be tested against the expected delay. The system will be tested at 50 Vp and 90 Vp. A change in color to the Push button will indicate when the program has released access to the user.

Diagnostic Mode (B-mode and Doppler): There are no additional risks associated with the diagnostic delivery (B-mode and Doppler) of ultrasound (US) than occurs with conventional US systems.

Device-related: The 3D ultrasound device under development is comprised of three commercially-available off-the-shelf components: a Verasonics ultrasound imaging system, an ultrasound transducer, and a motorized rotary stage. The Verasonics imager (Model V-1, Verasonics Inc., Kirkland, WA) is a research instrument that has previously received IRB approval within the UW for use below FDA limits for acoustic output intensities. The ultrasound transducer (P4-2, Philips Ultrasound, Bothell, WA) is an FDA-cleared device purchased from a compliant source in 'used' condition. The rotary stage (RTHM-190, IntelLiDrives Inc., Philadelphia, PA) is a commercial device designed for rotation of optical laboratory components.

The equipment is inspected (annually) by the University of Washington Scientific Instruments Division for electrical safety. This includes an evaluation of electrical leakage from each individual piece of equipment and the transducer, ground impedance, and line isolation. System operators will conduct a visual check of the equipment, ultrasound transducer, and electrical connections prior to starting the system to verify the system is in good operating order.

Breach of Confidentiality: There is a potential risk of breach of confidentiality. See data security protections in 9.6.

10.2 Reproductive risks. Are there any risks of the study procedures to men and women (who are subjects, or partner of subjects) related to pregnancy, fertility, lactation or effects on a fetus or neonate?

Examples: direct teratogenic effects; possible germline effects; effects on fertility; effects on a woman's ability to continue a pregnancy; effects on future pregnancies.

No \rightarrow If no go to question 10.3

Yes → If yes, answer the following questions:

a. Risks. Describe the magnitude, probability, duration and/or reversibility of the risks.

	probability, or duration of these risks.
	Examples: inform the subjects about the risks and how to minimize them; require a pregnancy test befor and during the study; require subjects to use contraception; advise subjects about banking of sperm and ova.
	If you will require the use of contraception: describe the allowable methods and the time period when contraception must be used.
	c. Pregnancy. Describe what you will do if a subject (or a subject's partner) becomes pregnant
	For example; will you require the subject to immediately notify you, so that you can discontinue or modige the study procedures, discuss the risks, and/or provide referrals or counseling?
Unforese	eable risks. Are there any research procedures that may have risks that are currently unforeseeable?
	sing a drug that hasn't been used before in this subject population.
X No	
Yes	→ If yes, identify the procedures.
Yes	→ If yes, identify the procedures.
	→ If yes, identify the procedures. who will be under regional or general anesthesiology. Will any research procedures occur while
Subjects v subjects-p	who will be under regional or general anesthesiology. Will any research procedures occur while patients are under general or regional anesthesia, or during the 3 hours preceding general or regional
Subjects v subjects-p	who will be under regional or general anesthesiology. Will any research procedures occur while
Subjects v subjects-p anesthesis	who will be under regional or general anesthesiology. Will any research procedures occur while patients are under general or regional anesthesia, or during the 3 hours preceding general or regional (supplied for non-research reasons)?
Subjects v subjects-p anesthesia	who will be under regional or general anesthesiology. Will any research procedures occur while patients are under general or regional anesthesia, or during the 3 hours preceding general or regional
Subjects v subjects-p anesthesia	who will be under regional or general anesthesiology. Will any research procedures occur while patients are under general or regional anesthesia, or during the 3 hours preceding general or regional a (supplied for non-research reasons)?
Subjects versus subjects per subjects per subjects per subjects per subjects versus per subjects versus per subjects per subjects versus per subjects per subject	who will be under regional or general anesthesiology. Will any research procedures occur while patients are under general or regional anesthesia, or during the 3 hours preceding general or regional a (supplied for non-research reasons)? If yes, check all the boxes that apply.
Subjects v subjects-p anesthesis	who will be under regional or general anesthesiology. Will any research procedures occur while patients are under general or regional anesthesia, or during the 3 hours preceding general or regional a (supplied for non-research reasons)? If yes, check all the boxes that apply. Administration of any drug for research purposes
Subjects v subjects-p anesthesis	who will be under regional or general anesthesiology. Will any research procedures occur while patients are under general or regional anesthesia, or during the 3 hours preceding general or regional a (supplied for non-research reasons)? If yes, check all the boxes that apply. Administration of any drug for research purposes Inserting an intra-venous (central or peripheral) or intra-arterial line for research purposes Obtaining samples of blood, urine, bone marrow or cerebrospinal fluid for research purposes
Subjects v subjects-p anesthesis	who will be under regional or general anesthesiology. Will any research procedures occur while patients are under general or regional anesthesia, or during the 3 hours preceding general or regional as (supplied for non-research reasons)? If yes, check all the boxes that apply. Administration of any drug for research purposes Inserting an intra-venous (central or peripheral) or intra-arterial line for research purposes Obtaining samples of blood, urine, bone marrow or cerebrospinal fluid for research purposes Obtaining a research sample from tissue or organs that would not otherwise be removed during surgery
Subjects v subjects-p anesthesis	who will be under regional or general anesthesiology. Will any research procedures occur while patients are under general or regional anesthesia, or during the 3 hours preceding general or regional as (supplied for non-research reasons)? → If yes, check all the boxes that apply. ☐ Administration of any drug for research purposes ☐ Inserting an intra-venous (central or peripheral) or intra-arterial line for research purposes ☐ Obtaining samples of blood, urine, bone marrow or cerebrospinal fluid for research purpos ☐ Obtaining a research sample from tissue or organs that would not otherwise be removed during surgery ☐ Administration of a radio-isotope for research purposes**
Subjects v subjects-p anesthesis	who will be under regional or general anesthesiology. Will any research procedures occur while patients are under general or regional anesthesia, or during the 3 hours preceding general or regional at (supplied for non-research reasons)? If yes, check all the boxes that apply. Administration of any drug for research purposes Inserting an intra-venous (central or peripheral) or intra-arterial line for research purposes Obtaining samples of blood, urine, bone marrow or cerebrospinal fluid for research purposes Obtaining a research sample from tissue or organs that would not otherwise be removed during surgery

If you checked any of the boxes:

You must provide the name and institutional affiliation of a physician anesthesiologist who is a member of your research team or who will serve as a safety consultant about the interactions between your research procedures and the general or regional anesthesia of the subject-patients. If your procedures will be performed at a UW Medicine facility or affiliate, the anesthesiologist must be a UW faculty member.

[name]; University of Washington

- ** If you checked the box about radio-isotopes: you are responsible for informing in advance all appropriate clinical personnel (e.g., nurses, technicians, anesthesiologists, surgeons) about the administration and use of the radio-isotope, to ensure that any personal safety issues (e.g., pregnancy) can be appropriately addressed. This is a condition of IRB approval.
- **10.5 Data and Safety Monitoring**. A Data and Safety Monitoring Plan (DSMP) is required for clinical trials (as defined by NIH). If required for your research, upload your DSMP to the **Supporting Documents** SmartForm in **Zipline**. If it is embedded in another document you are uploading (for example, a Study Protocol, use the text box below to name the document that has the DSMP.

N/A

10.6 Un-blinding. If this is a double-blinded or single-blinded study in which the participant and/or you do not know the group to which the participant is assigned: describe the circumstances under which un-blinding would be necessary, and to whom the un-blinded information would be provided.

N/A

- **10.7 Withdrawal of participants.** If applicable, describe the anticipated circumstances under which participants will be withdrawn from the research without their consent. Also, describe any procedures for orderly withdrawal of a participant, regardless of the reason, including whether it will involve partial withdrawal from procedures and any intervention but continued data collection or long-term follow-up.
 - Subjects may also be discontinued by the study coordinator or physician because of an adverse event or other event related to the subject's health or welfare. Subjects may be discontinued from the study because their stone could not be identified on ultrasound. Subjects discontinued prior to the investigational treatment will not be counted as an enrollment and no further data will be collected.
- **10.8** Anticipated direct benefits to participants. If there are any direct research-related benefits that some or all individual participants are likely to experience from taking part in the research, describe them below:

Do not include benefits to society or others, and do not include subject payment (if any). Examples: medical benefits such as laboratory tests (if subjects receive the results); psychological resources made available to participants; training or education that is provided.

None

- 10.9 Individual subjects findings.
 - **a**. Is it likely that your research will unintentionally discover a previously unknown condition such as a disease, suicidal intentions, or genetic predisposition?

No X Yes →	If yes, explain whether and how you would share the information with the subject.
	It is possible that the diagnostic ultrasound imaging will detect disease that was previously unknown. If the sonographer detects something abnormal, the images will be saved and either a dedicated genitourinary radiologist or one of the clinical urologists will review the images and inform the subject of any potential disease.
	routinely share the individual results of your study procedures with the subjects – such as sults, laboratory tests, etc.?
X No Yes →	If yes, complete and upload the SUPPLEMENT: Participant Results Sharing to the Supporting

10.10 Commercial products or patents. If a commercial product or patent could result from this study, describe whether subjects might receive any remuneration/compensation and, if yes, how the amount will be determined:

If a commercial product or patent could result from this study, subjects will not receive any remuneration/compensation.

Documents SmartForm of **Zipline**

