HSD may ask for documentation of the externally-imposed urgency. A higher priority should not be requested to compensate for a researcher's failure to prepare an IRB application in a timely manner. Note that IRB review requires a certain minimum amount of time; without sufficient time, the IRB may not be able to review and approve an application by a deadline.

)	No	
	Yes	→ If yes, briefly describe the urgency or deadline as well as the reason for it.

1.5 Objectives Using lay language, describe the purpose, specific aims, or objectives that will be met by this specific project. If hypotheses are being tested, describe them. You will be asked to describe the specific procedures in a later section.

If your application involves the use of a HUD "humanitarian" device: describe whether the use is for "on-label" clinical patient care, "off-label" clinical patient care, and/or research (collecting safety and/or effectiveness data).

Specific questions this research project is designed to answer:

- 1. How well are stones of different types seen by two standard ultrasound techniques (B-mode and Doppler)?
- 2. How accurate is the measurement of stone size on ultrasound?
- 3. How accurate is ultrasound at detecting stones?
- 4. Can ultrasound reliably detect stones smaller than 2 mm?
- 5. How much do stones and stone pieces move during lithotripsy treatment?

1.6 Study design. Provide a one-sentence description of the general study design and/or type of methodology.

Your answer will help HSD in assigning applications to reviewers and in managing workload. Examples: a longitudinal observational study; a double-blind, placebo-controlled randomized study; ethnographic interviews; web scraping from a convenience sample of blogs; medical record review; coordinating center for a multi-site study.

Observational study examining the accuracy of ultrasound imaging.

(1.7) Intent. Check all the descriptors that apply to your activity. You must place an "X" in at least one box.

This question is essential for ensuring that your application is correctly reviewed. Please read each option carefully.
Descriptor
1. Class project or other activity whose purpose is to provide an educational experience for the researcher (for example, to learn about the process or methods of doing research).
2. Part of an institution, organization, or program's own internal operational monitoring.
le l

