→ If yes, describe what you will do, for each of these subject groups, to reduce any effect of the setting or relationship on their decision.

Examples: a study coordinator will obtain consent instead of the subjects' physician; the researcher will not know which subjects agreed to participate; subjects will have two days to decide after hearing about the study.

Patients will mainly be recruited in the PI's clinics. In order to reduce any effect of the setting or relationship on their decision, the PI will not be consenting the patients for the research study. The patients will be informed that their standard care will not be affected by their decision of whether or not to participate. They will also be told that participating in this research study is completely voluntary and that they may end their participation at any time.

e. Ongoing process. For research that involves multiple or continued interaction with subjects over time, describe the opportunities (if any) you will give subjects to ask questions or to change their minds about participating.

T A	1	
1	/	/\

have already b	peen addressed in question 4.	6 .		
	fication of the individual's signat	tronically is not considered written consent unless it is obtained. In other words, saying "yes" by email is rarely conside	-	
a. Are you obt	aining written documentation	n of consent for:		
None of	your research procedures	→ Use the table below to provide your justification question 8.4.	on then go	to
X All of yo	ur research procedures	→ Do not complete the table; go to question 8.4.	.	
Some of	your research procedures	Use the table below to identify the procedures not obtain written documentation of consent subjects.		•
Adult subject group ¹		res or data/specimen collection (if any) for ill be NO documentation of consent	Will provide with a v stater describe resea (option	them written ment ing the arch
Table footnotes 1. If your answer in procedures.	is the same for all adult groups o	r all procedures, you can collapse your answer across the	groups and/	′or
	peaking or -reading adult sub r literacy in English?	pjects. Will you enroll adult subjects who do not spea	ak English o	r who
X No Yes →	them during the consent pro-	ou will use to ensure that the oral and written inforn cess and throughout the study will be in a language (for written materials such as consent forms or ques hension level.	readily	
07/21/2025				#2003

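### Section 10.7 makes a stone that ultrasound misses a reason for discontinuation in a study of ultrasound detection, and ties counting and further data to an undefined treatment

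*Protocol*

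**What the plan says.** Section 1.6 gives the design as "Observational study examining the accuracy of ultrasound imaging". Among the five questions in Section 1.5, question 1 asks how well different stone types are seen on B-mode and Doppler, question 3 asks "How accurate is ultrasound at detecting stones", and question 4 asks "Can ultrasound reliably detect stones smaller than 2 mm".

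Under Section 2.2, subjects enter with at least one kidney stone and/or under treatment for stones. Section 5.1 compares ultrasound with CT from the medical record in Group 1 and with observation at surgery in Group 2.

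Section 10.7, on withdrawal, says: "Subjects may be discontinued from the study because their stone could not be identified on ultrasound". The next sentence reads: "Subjects discontinued prior to the investigational treatment will not be counted as an enrollment and no further data will be collected". The same section also allows discontinuation for an adverse event or for the subject's health or welfare. Section 8.2 says subjects are told that "they may end their participation at any time".

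No section defines the investigational treatment. Section 1.3 says that in this study the device only images. Section 10.1 nevertheless describes testing the output of a Push pulse.

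**The concern.** A stone that the reference standard shows and the study scan does not identify is a false negative. In a detection study that result has to be counted. Section 10.7 makes it a permitted reason to end participation, so whether a subject stays in the study can depend on the result of the test being evaluated.

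The following sentence adds to the problem, because its reach depends on an undefined term. If misses leave the data while hits remain, sensitivity rises. That would affect questions 3 and 4 directly, and also question 1, where poorly seen stone types would be under-represented. Small stones may be the most exposed if they are harder to see. If reference data are not collected after a failed scan, a later analysis rule cannot recover those misses unless someone goes back to the records.

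**Working it through.** **The two readings of the counting sentence.**

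- *The term means the study scan.* A subject whose stone was missed on that scan has already passed the point, so the sentence does not reach that subject. The discontinuation remains, and Section 10.7 does not say what is still collected afterwards.
- *The term means a treatment that this imaging-only study does not give.* No subject ever passes the point. Every subject discontinued for an unseen stone is then uncounted, with no further data.

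**What could be lost.** In both groups Section 5.1 has existing images saved from the record, so a miss may already have scan and reference on file. In Group 2 the scan takes place during surgery. Endoscopic video, fluoroscopy and any stone chemistry come from routine care and would still exist, but might not be abstracted after a failed scan.

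**Size, by illustration.** The protocol states no sensitivity, so there is no figure to reproduce. The following are assumptions: true per-stone sensitivity *s*; *k* stones per subject; and *f*, the share of subjects with no stone seen who are dropped from the analysis. If stones within a subject are detected independently, the dropped subjects contribute only misses, so

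apparent sensitivity = s / (1 − f(1 − s)^k).

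For s = 0.7, f = 0.5, k = 1: 0.7 / (1 − 0.5 × 0.3) = 0.7 / 0.85 = 82.4%.

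| s | f | k = 1 | k = 2 | k = 3 |
|---|---|---|---|---|
| 70% | 10% | 72.2% | 70.6% | 70.2% |
| 70% | 25% | 75.7% | 71.6% | 70.5% |
| 70% | 50% | 82.4% | 73.3% | 71.0% |
| 50% | 50% | 66.7% | 57.1% | 53.3% |
| 90% | 50% | 94.7% | 90.5% | 90.0% |

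**Compared with sampling error.** Section 2.7 mentions 170 approved subjects and about 200 more: 170 + 200 = 370. This indicates scope and is not a limit; it also pools two groups with different reference standards. With k = 1 and s = 0.7, 259 subjects are seen and 111 missed. The 95% half-width is 1.96 × √(0.7 × 0.3 / 370) = 4.7 points. Dropping 24 of the 111 gives 259 / 346 = 74.9%, a shift of 4.9 points, which exceeds the half-width. At s = 0.9 this takes 13 of 37 misses (333 / 357 = 93.3%, half-width 3.1 points). At s = 0.5 it takes 35 of 185 (185 / 335 = 55.2%, half-width 5.1 points).

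**Several stones per subject.** Under independence with k = 3 and s = 0.7, dropping every subject with no stone seen gives 0.7 / (1 − 0.027) = 71.9%. That shift of 1.9 points is below the half-width of 1.96 × √(0.21 / 1110) = 2.7 points.

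The result depends on independence. Under a beta-binomial model with intra-subject correlation ρ, the parameters sum to 1/ρ − 1. At ρ = 0.1 the sum is 9 and the miss parameter is 2.7, so the chance that all three stones are missed is (2.7 × 3.7 × 4.7) / (9 × 10 × 11) = 0.047. The largest apparent sensitivity is 0.7 / 0.953 = 73.5%, a shift of 3.5 points. The cluster-adjusted half-width is 1.96 × √(0.21 × 1.2 / 1110) = 3.0 points. At ρ = 0.05 the shift is 2.7 against 2.8, and at ρ = 0.3 it is 7.4 against 3.4, with the half-width reached at f of about 49%.

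**The case against.** The strongest objection is that not counting someone as an enrollment is an accrual statement, made in answer to an ethics-form question on withdrawal. It is not an analysis-set definition. A reader might infer from Section 10.7 that missed stones are excluded from the sensitivity denominator. The protocol does not say so, and a SAP could keep those subjects. The rule is also permissive, and the ban on data applies only to further data: images and raw signals from the scan are already saved, and an existing CT may be too. This stands, and it makes the bias conditional. It does not remove the conflict between Sections 10.7 and 1.5, because a SAP can analyse only data that were kept or abstracted.

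Second, not every unidentified stone is a false negative. Group 1 is compared with a CT already in the record, and no interval between CT and scan is stated. A stone that passed or moved in between would be scored wrongly as a miss, which biases sensitivity downward. This also stands, and the remedy must allow for it.

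Third, Section 10.7 does not say which ultrasound it means. The record may contain clinical ultrasound as well, and the point made here concerns the study scan.

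Finally, a reader might conclude that three or more stones per subject make the rule harmless. That follows only if stones within a subject are detected nearly independently, and the protocol gives no basis for assuming so.

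**Conclusion.** The point holds as a conditional risk that the protocol's own wording creates. A negative result on the test under study is a permitted reason for discontinuation, and the sentence on counting and further data depends on a term that has no meaning in an imaging-only study. If the rule is used, and if the uncounted status is carried into the analysis or later reference data are not abstracted, sensitivity is biased upward.

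The document does not show that this has happened, and the size cannot be derived from it. The 82.4% against a true 70% assumes one stone per subject and half of the missed subjects dropped. The effect shrinks with more stones per subject, by an amount that depends on within-subject correlation. The wording should be corrected, with medium confidence that the rule matters in practice.

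**What to change.** Remove non-visualisation on study ultrasound as a reason for discontinuation, or state that it does not take the subject out of the accuracy analysis. Add:

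> Once study ultrasound has been started, the subject's scan result is kept and reference data are still collected within the subject's consent. A reference-standard stone that is not identified is recorded as not detected and stays in the denominator for questions 1, 3 and 4. Where the reference imaging predates the scan and the stone's presence at the scan is not verified, this is flagged and examined in a sensitivity analysis.

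Define or delete the investigational treatment so that Sections 1.3, 10.1 and 10.7 agree. Report, as far as records allow, how many subjects were already discontinued for this reason. Leave discontinuation for adverse events, welfare or the subject's own choice unchanged.

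The cost is a protocol modification, with no new study procedures. Counting past discontinuations is limited to existing records and may need IRB review. Reported sensitivity may be lower.
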